- To determine factors, including inter-site variability, influencing surgical referral and acceptance rates for air leak and recurrence management
- To determine factors influencing short-term recurrence rates

Research questions which may be addressed as part of the study are listed below.

CLINICAL OUTCOMES

- 1. What are the demographics of the SSP population in the UK (age, gender, underlying aetiology, previous SSP, lung function)?
- 2. What are the size and location of pneumothorax on chest x-ray (side, maximum intrapleural distance, hilar intrapleural distance)?
- 3. How are the patients managed during their inpatient stay (initial management, prolonged air leak management, recurrence prevention interventions, surgical referral, surgical intervention)?
- 4. What are the patients' length of stay?
- 5. What are the patients' duration of air leak?
- 6. What are the patients' mortality rate?
- 7. What proportion are referred and receive surgery?
- 8. What are the patients 6-month ipsilateral recurrence rates?
- 9. What is the expertise available at hospital (presence of onsite thoracic surgical unit, dedicated pleural clinic)?

METHODOLOGY

STUDY DESIGN

LISP is a multi-centre, prospective, longitudinal cohort study of patients diagnosed with SSP.

STUDY POPULATION

Population of interest: patients presenting to hospital with secondary spontaneous pneumothorax.

Inclusion

Emergency attendance to hospital with secondary spontaneous pneumothorax, confirmed by radiology, with SSP defined as:

- spontaneous pneumothorax in presence of known or suspected lung disease OR
- spontaneous pneumothorax in patient \geq 50 years of age and smoking history.

Exclusion

- age <16 years of age
- iatrogenic pneumothorax
- traumatic pneumothorax

RECRUITMENT

Recruitment procedure

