Research in an emergency setting is always challenging due to high clinical work load and the proportion of eligible patients presenting out of hours. Clinicians have additional levels of clinical demand during night shifts and research teams are often not available to support recruitment. Additionally, patients with SSP will potentially be in significant pain/respiratory distress at the time of presentation and may have diminished capacity. However, it is vital that patients presenting out of hours with SSP are offered the opportunity to participate in this research, and it is also vital to the integrity of the research methodology that these patients are included within a consecutive sample, to ensure the findings are generalizable.

To minimize the risk of recruitment bias in our sample, this study plans to recruit 24 hours a day, 7 days a week, at all sites. To achieve this, there will be extensive departmental awareness of the study raised at each site, and we will use trained clinicians to recruit to the study as part of routine care, in addition to research teams. As such, it is essential that we minimize the administrative burden for these busy clinicians. We have chosen an opt-out consent process to facilitate this, designed to ensure patients are robustly informed and provided with tiered opportunity to ask questions/engage with the research at their preference. This method will minimize the risk of

missing a significant cohort of patients presenting between 2200 and 0800, minimize the burden on clinical staff recruiting during standard working hours, but maximise the generalisability of the research.

This study involves no change in clinical treatment and no additional interventions for participants. It therefore carries no clinical risk. It is also well recognised that patients attending the ED with SSP are in pain and at a time of acute anxiety/distress; often, they require immediate management. As such it will be impractical and potentially distressing to seek fully informed consent in an emergency setting. We will therefore adopt a proportionate approach using an opt-out strategy, as supported by the Health Research Authority (HRA).

Participation in LISP will not impact on any part of the patients' routine care and they will be entitled to withdraw from the study at any point, without giving a reason.

FIGURE 1: OPT-OUT CONSENT FLOW CHART

RECRUITMENT TARGET

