A conservative estimate of patients with SSP presenting and identified by research staff at each site is 12 per annum (based on Hi-Spec RCT screening log(6)). Provisional anonymised HES data suggest that this may be a

considerable underestimate, demonstrating a mean of 40.5 SSP presentations/annum at the top 15 NHS Trusts. As SSP typically have substantial inpatient length of stay and are managed by Respiratory team, high identification rates are anticipated. Additionally, the opt-out consent model should maximize data capture. With 20 participating sites, we would expect a minimal of 120 patients over a 6-month period.

The recruitment target is a minimum of 120 patients per year. The LISP will run over a one-year period (recruiting for 6 months with a 6 month follow up period). Given the observational nature of this study, patients will be eligible to co-enrol in other studies if invited.

FOLLOW-UP SCHEDULE

All participants will only undergo assessment at a single time point, at enrolment ("baseline assessment"). This will be performed by a member of the study team and should be done within the first week from enrolment.

Subsequently, study data will be acquired from the medical records at two further time points, at 1-month and 6-months post enrolment. This will be conducted by the local medical research investigator. As this is a trainee-lead project, it is anticipated this will a respiratory trainee.

LONGITUDINAL INVESTIGATION OF SECONDARY PNEUMOTHORAX (LISP) PATIENT JOURNEY FLOWCHART **INSPIRE NETWORK**

Emergency attendance to hospital with secondary spontaneous pneumothorax, confirmed by radiology, with

- · spontaneous pneumothorax in presence of known or suspected lung disease
- spontaneous pneumothorax in patient ≥50 years of age and smoking history.
- iatrogenic pneumothorax
- traumatic pneumothorax

FIGURE 2: PATIENT JOURNEY FLOWCHART

DATA COLLECTION

Baseline assessment

The baseline assessment for all patients will incorporate routinely collected clinical information, such as:

- History and examination by a Respiratory physician, including duration of symptoms, co-morbidities and • past medical history, current/recent medications, smoking status including cannabis, clinical frailty score (CFS) and performance status (PS).
- CXR data- size of pneumothorax

1-month post-enrolment (+/- 14 days)

A review of participant's clinical records to collect data on key clinical outcomes, including but not exclusively, the:

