further/additional patient information, including a PIS to be mailed to a home address or research nurse contact (face to face if in hospital, or by telephone). Each patient will have a unique study number. The opt-out log will be checked for a final time 4 weeks after data-collection has finished. For patients who choose to opt-out from the study, the only information that will be kept on the opt-log will be their name, date of birth and a corresponding study number. The opt-out log will be cross-referenced with the central REDCAP database using this study number. The opt-out log will only be kept at local site, any only accessible to usual care team.

This approach, targeted to the individual, is considered to constitute active recruitment as per paragraph 21 of the NIHR Clinical Research Network (CRN) recruitment policy document(7)

In addition, this methodology for observational research has been used with ethical approval and CRN portfolio adoption/accrual for multiple ED projects, including the PAT-POPS study, the AHEAD, the HEAD study, and most recently, the SHED study (12-16)

FINANCE AND INSURANCE

The study has been funded through an unrestricted research grant provided by Rocket Medical.

This is an NHS-sponsored research study. For NHS sponsored research HSG(96)48 reference no. 2 refers. If there is negligent harm during the clinical trial when the NHS body owes a duty of care to the person harmed, NHS Indemnity covers NHS staff, medical academic staff with honorary contracts, and those conducting the trial. NHS Indemnity does not offer no-fault compensation and is unable to agree in advance to pay compensation for non-negligent harm. Ex-gratia payments may be considered in the case of a claim.

REPORTING AND DISSEMINATION

A plain English summary will be prepared and disseminated with the help of our PPI group, including via social media, and provided to trial participants. We will report our results via a high-impact medical journal and present findings at international respiratory and conferences.

This study is supported by the INSPIRE (INtegrated reSPIratory REsearch) collaborative, a respiratory trainee work which aims to facilitate a collaborative approach to performing clinical research projects and high-quality audits at regional and national scale for the benefit of patients with respiratory disease. The study results will be published on the INSPIRE website and at INSPIRE events.

References

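### The cohort is meant to be consecutive, but identification leans partly on long inpatient stay and nothing counts the eligible patients who are missed, so length of stay may be overstated by an unknown amount

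*Protocol*

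**What the plan says.** Under Study population, the unit of eligibility is the attendance: "Emergency attendance to hospital with secondary spontaneous pneumothorax, confirmed by radiology, with SSP defined as", followed by the two definitions of SSP. No admission or minimum stay is required.

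Under Recruitment procedure, speaking of patients who present out of hours, the protocol calls it vital to the integrity of the method that "these patients are included within a consecutive sample, to ensure the findings are generalizable". It plans round-the-clock recruitment at all sites, by trained clinicians as well as research teams.

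Under Recruitment target, it gives two reasons for expecting good capture, long stay and respiratory-team care: "As SSP typically have substantial inpatient length of stay and are managed by Respiratory team, high identification rates are anticipated". The planning figure is "A conservative estimate of patients with SSP presenting and identified by research staff at each site is 12 per annum", taken from another trial's screening log. The protocol says this may be a "considerable underestimate, demonstrating a mean of 40.5 SSP presentations/annum at the top 15 NHS Trusts".

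Under Consent, the information sheet is offered at clinical assessment. An inclusion checklist records that it was given. The opt-out log is compared with the checklists and the REDCap database at three time points. Patients deemed eligible and not on the opt-out log are included. Sites may also offer "further/additional patient information, including a PIS to be mailed to a home address or research nurse contact".

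Under Follow-up schedule, the baseline assessment is timed from enrolment. No limit is stated on the time from presentation to enrolment.

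**The concern.** A patient missed at the door can be picked up later, but by the route described under Recruitment target this happens mainly while the patient is still in hospital, and mainly on a respiratory ward. The chance of being found by that route rises with length of stay, which is itself a listed outcome. Patients aspirated and sent home, managed in ambulatory care, or dead within a day or two are the most exposed to being missed. The protocol expects some such patients, since it collects aspirations and ambulatory care among the interventions.

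The Recruitment procedure section itself says that research teams are often unavailable out of hours and that night clinicians carry extra demand, so capture at presentation is unlikely to be complete. The three records that are cross-checked (checklist, opt-out log, database) all begin with a patient who has been recognised. Comparing them cannot reveal someone who is in none of them.

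The Background says UK data on SSP are absent, including basic figures for length of stay and surgical referral. LISP's figures would therefore be likely to serve as the UK reference. If short stays are under-represented, the length of stay is too high, and a reader would have no capture fraction by which to judge how far.

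**Working it through.** **1. The protocol's own figure.** Inputs from Recruitment target: 20 sites, 12 identified per site per year, 6 months.

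20 × 12 × 0.5 = 120, which reproduces "With 20 participating sites, we would expect a minimal of 120 patients over a 6-month period".

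**2. What the planning figures can and cannot show.** With 40.5 presentations per year at every site, 20 × 40.5 × 0.5 = 405, and 12 / 40.5 = 0.296. This is not a capture rate. The 12 is called conservative and the 120 is a minimum. The 40.5 is a mean for the top 15 Trusts, not for the 20 sites. The Background also says HES does not separate primary from secondary pneumothorax, so 40.5 is an uncertain denominator. The figures leave room for incomplete capture and show no more than that.

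**3. Size of the possible bias in length of stay.** The documents give no capture rate by length of stay, so everything here is assumed:
- true stay T lognormal, median 7 days, SD of log 0.8;
- a fraction a is found at presentation, whatever the stay;
- anyone else is found with probability p on each inpatient day.

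P(found | T) = a + (1 − a) × [1 − (1 − p)^ceil(T)]

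The observed median is the median of T weighted by this probability.

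| Found at presentation (a) | p per day | Total found | Observed median (days) | Overstatement |
|---|---|---|---|---|
| 0% | 10% | 56% | 9.6 | about 37% |
| 0% | 20% | 77% | 8.4 | about 21% |
| 0% | 40% | 93% | 7.5 | about 7% |
| 50% | 10% | 78% | 7.9 | about 13% |
| 50% | 20% | 89% | 7.6 | about 9% |
| 50% | 40% | 96% | 7.2 | about 3% |
| 70% | 10% | 87% | 7.5 | about 7% |
| 70% | 20% | 93% | 7.4 | about 5% |
| 70% | 40% | 98% | 7.1 | about 2% |
| 90% | 10% | 96% | 7.1 | about 2% |

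If P(found | T) does not depend on T, the weights are constant and the bias is zero at any capture rate.

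In the worst row (a = 0, p = 10%), stays of 2 days or less fall from Φ((ln 2 − ln 7)/0.8) = 5.9% of all patients to 1.9% of those found.

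**4. Surgery proportion.** Assume that surgery occurs only in longer-stay patients and that these are captured at 95%. Let s be the true share of short stays and c their capture. The surgery proportion is then inflated by the factor 0.95 / [s × c + (1 − s) × 0.95].
- c = 80%: 1.03 (s = 20%) to 1.05 (s = 30%)
- c = 50%: 0.95 / 0.86 = 1.10 (s = 20%) to 0.95 / 0.815 = 1.17 (s = 30%)

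The documents do not show that surgery or air-leak duration tracks stay. It is plausible, but it is an assumption.

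**The case against.** The sentence about long stays is a feasibility remark in support of the target. It is not the recruitment rule, it predicts high identification, and it gives respiratory-team care as a second reason. The actual procedure is designed against this bias: recruitment at all hours, trained clinicians, information at the point of assessment, opt-out consent, and inclusion of every eligible patient who has not opted out. Outcomes come from records, so an early discharge or death does not bar a patient who has been recognised. The two flowcharts are not fully visible in the text available, and how capture is reported can be left to an analysis plan.

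Much of this stands. A reader might infer that the cohort is enriched for long stays and its results biased upward as a matter of fact. The documents do not support that: they give no capture rate by stay, and with good capture at presentation the effect is a few per cent. A reader might also take 12 against 40.5 as evidence that 70% of patients will be missed; step 2 of the working shows why it is not. The 37% figure needs no capture at presentation at all, contrary to the stated procedure.

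What does not stand is that the safeguards close the gap. Round-the-clock recruitment is an intention, and the written cross-checks cannot show whether it was met. Nor can this be left wholly to an analysis plan, because information on missed patients has to be gathered by the sites.

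**Conclusion.** The concern holds as an unmeasured risk. The protocol claims a consecutive sample of all emergency attendances, relies partly on long stay and respiratory-team care to find patients, and in the text shown has no step to recover or count those missed at presentation. Under the assumed model, the median stay is overstated by about 2% to 13% when 50% to 70% are found at presentation, by up to about 37% when none are, and not at all when capture is unrelated to stay. Any effect on air-leak duration and surgery depends on their tracking stay. Which case applies cannot be learned from the study as written. The change is worth making because length of stay is a core output and the remedy is cheap.

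**What to change.** - At a fixed interval, have the usual care team at each site reconcile the inclusion checklist against the emergency department or radiology list, or the discharge-coding list, of pneumothorax. The usual care team should do this because the protocol restricts identifiable data to them.
- Include eligible patients who have already been discharged through the opt-out route with a mailed information sheet, and take their outcomes from records. The Consent section now describes mailing only as additional information, so this use has to be written in.
- Record the dates of presentation and enrolment on the eCRF, and measure length of stay from presentation.
- Report the capture fraction by site, with an anonymised count of eligible patients not enrolled. Collect nothing further on patients who opt out, in line with the existing opt-out terms.
- Call the sample consecutive only if the capture fraction supports it.

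A delayed-entry analysis starting at enrolment is not a substitute. Patients enrolled after discharge would never be in the risk set, so the short stays just recovered would be lost again.

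The cost is modest site time for a periodic list check, which trainees already working on the study could do where they belong to the usual care team, plus two date fields. Clinical care does not change.

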UK specific data on SSP is entirely absent, with even basic data on typical length of stay, underlying aetiology and surgical referral rates having to be extrapolated from international studies out of necessity. Currently, a single centre study from Japan and a French epidemiological study provide the best estimates for length of stay in SSP(2, 3). National databases, such as the Hospital Episode Statistics (HES) database, do not distinguish between PSP and SSP, and do not provide detailed individual patient level data.

British Thoracic Society (BTS) guidelines provide clear advice on different treatment strategies for primary (PSP) and secondary (SSP) spontaneous pneumothorax, but compliance with these guidelines amongst non-respiratory healthcare professionals is reportedly low(8). Additionally, the advice on SSP is based on limited data and there are many outstanding research questions that need answering. There is no current guidance on patient selection for surgical management for persistent air leak (PAL) and recurrence prevention. Patients with SSP are typically felt to be poor surgical candidates, due to poor physiological reserves and comorbidities, but there is a lack of information about which patients would most benefit and which are most are risk. This project would identify the patient characteristics of those accepted for surgery, and their outcomes. Additionally, the management of persistent air leak is extremely problematic in this patient cohort, with no clear evidence on how best to manage. This project would capture current national practice on PAL and the impact this had on air leak duration.

Recurrence rates are felt to be higher in SSP compared to PSP, with historic and poorly evidenced cited rates between 40-50%(5), however there is no robust data to inform on this, or the factors which influence it. This project would give vital insights and help inform practice.

10

AIMS & OBJECTIVES:

To determine the characteristics, healthcare burden, management, and outcomes of secondary spontaneous pneumothorax (SSP) in UK over a 1-year period

AIMS AND OBJECTIVES:

- To determine characteristics of SSP patients admitted in study period (age, gender, underlying respiratory condition)
- To determine management of SSP in study period (procedures, recurrence prevention, surgery)
- To determine outcomes of SSP admission (length of stay, duration of air leak, mortality)

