- Initial length of stay
- Digital air leak (DAL) measurement (if available)
- Analogue air leak assessment
- Number of type of interventions, including therapeutic aspirations, intercostal chest drains (ICD) insertions, blood batch, ambulatory care and surgical procedures.
- Treatment complication
- Mortality

6 month post-enrolment (+/- 14 days)

A review of participant's clinical records to collect data to identify:

- Initial Length of stay (if exceeded 1 month)
- Ipsilateral recurrence of pneumothorax

STUDY FLOW CHART:

Schedule of assessments:

Description	Investigation	Baseline	4 -week	26-week
		assessment	follow up	follow up
			assessment	assessment
			(+/- 7 days)	(+/- 4
				weeks)

Clinical review	Patient demographics	Х		
	Pneumothorax history	Х		
	Patient co-morbidities	Х		
	Assessment of PS/CFS	Х		
	Medication history	Х		
	Number of interventions		Х	
	Mortality		Х	
	Length of stay		Х	Х
Recurrence			Х	Х
Imaging	CXR	Х		
	СТ		X*	
Air leak	Analogue air leak assessment (if		Х	
assessment	available)			
	Digital air leak assessment (if		Х*	
	available)			
*-if clinically available				

DEFINITION OF END OF TRIAL

All participants will be actively followed up for 6 months after recruitment. The opt-out log will be reviewed 4 weeks after data-collection has finished. The end of the trial as a whole will be after all trial participants have completed follow up, all data queries have been resolved, the database locked and the analysis completed.

DATA HANDLING AND RECORD KEEPING

Data collection tools and source document identification

Source data will all be electronic from NHS Trust computer systems i.e., patients' medical records, laboratory and radiology reports and directly entered onto an eCRF in REDCap.

Data handling and record keeping

Data entry at will use a bespoke study database housed on the University of Bristol server, built using the validated open-source REDCap system and regularly backed up. The study investigator will facilitate data entry into the database via an electronic case report form (eCRF) with the support of the clinical team. Each participant will be allocated an unambiguous subject identification code (trial participant ID).

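### Surgery and pleural procedures are recorded only to the 1-month review, although the surgery objectives carry no such limit, and readmission bed-days are not recorded at all

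*Protocol*

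**What the plan says.** **What the study sets out to determine.** The lead objective in the Protocol (Aims & Objectives) is "To determine the characteristics, healthcare burden, management, and outcomes of secondary spontaneous pneumothorax (SSP) in UK over a 1-year period". Below it stand:

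- a management objective: "To determine management of SSP in study period (procedures, recurrence prevention, surgery");
- an outcomes objective: "To determine outcomes of SSP admission (length of stay, duration of air leak, mortality");
- a surgical objective on factors, including differences between sites, "influencing surgical referral and acceptance rates for air leak and recurrence management".

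Under Clinical outcomes, question 3 asks "How are the patients managed during their inpatient stay". Question 7 asks "What proportion are referred and receive surgery" and gives no time frame. Under Analyses, surgical management is one of the outcomes to be modelled by logistic regression.

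**What is collected.** Under Data collection, the 1-month review takes initial length of stay, air leak, interventions (the item ends with "ambulatory care and surgical procedures"), complications and mortality. That list is introduced as non-exhaustive. The 6-month review has two items: "Initial Length of stay (if exceeded 1 month") and ipsilateral recurrence. It carries no such open wording. The schedule of assessments agrees. The interventions row has one mark, at 4 weeks, as does mortality. Length of stay and recurrence are marked at 4 and 26 weeks.

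**The concern.** The surgical questions are wider than the data meant to answer them. Surgery to prevent recurrence, or for a recurrence itself, can fall well after the first month, and the protocol names recurrence management as a reason for surgical referral. Followed as written, a patient operated on at three months enters the data set as not having had surgery.

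Three results are at stake:

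- The question 7 proportion, read over the 6-month follow-up, can only be too low.
- In the model for surgical management, late-surgery patients are coded as non-surgical. If late surgery is related differently from early surgery to the evaluated parameters, the estimated associations change. The same applies to the comparison between sites: where access to surgery is slower, more of it falls outside the recorded window.
- Procedures to prevent recurrence that take place after the 1-month review are also unavailable when factors influencing recurrence are studied.

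Separately, neither review collects admission and discharge dates for readmissions. Any result reported under the burden heading therefore reflects the first admission only.

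**Working it through.** **The protocol's own figure.** Recruitment target: 20 sites × 12 patients per site per year × 0.5 year = 120. This reproduces the stated minimum. The point disputes no number in the protocol.

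**Objectives set against collected items.**

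| Aim or question | Time frame in the protocol | Collected to 1 month | Collected from 1 to 6 months |
|---|---|---|---|
| Management, including surgery | study period | interventions, surgery | nothing |
| Surgical referral and acceptance, including for recurrence | none stated | surgery; referral not named, but the list is open | nothing |
| Question 7 | none stated | as above | nothing |
| Length of stay | the SSP admission | initial stay | initial stay, if over 1 month |
| Recurrence (question 8) | 6 months | yes | yes |
| Healthcare burden | no measure defined | initial stay, interventions | initial stay only; no readmission days |

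The fourth row shows that the gap exists even within the index admission. For a patient still in hospital after the 1-month review, the stay is completed at 6 months but the procedures and surgery are not.

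**Share of follow-up without procedure collection.** Take 26 weeks = 182 days. The review falls at day 28 (schedule), at day 28 + 7 = 35 at the latest by the schedule's window, or at about day 30 + 14 = 44 at the latest by the text's window.

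- 1 − 28/182 = 85%
- 1 − 35/182 = 81%
- 1 − 44/182 = 76%

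This is a share of time, not of procedures, which are likely to cluster early.

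**Illustration for surgery (both inputs assumed).** Let p be the true 6-month surgery proportion and s the share of surgery done after the 1-month review. The observed proportion is p(1 − s). With p = 20%:

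- s = 10%: 18%, or 21.6 of 120 patients instead of 24
- s = 25%: 15%, or 18 of 120
- s = 50%: 10%, or 12 of 120

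On the same assumptions, two groups of sites with an identical 20% at 6 months would appear as 18% and 10% if only the timing of surgery differed (s = 10% and 50%).

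**Illustration for bed-days (assumed).** If a proportion r of patients recur, and each recurrence leads to exactly one admission as long as the first, the missed share of total bed-days is r/(1 + r):

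- r = 20%: 0.20/1.20 = 17%
- r = 25%: 0.25/1.25 = 20%
- r = 40%: 0.40/1.40 = 29%
- r = 50%: 0.50/1.50 = 33%

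The 20% and 25% are assumptions. The 40% to 50% is the rate cited in the Background, which the protocol itself calls poorly evidenced and gives without a time horizon. For 6 months it is at most an upper illustration. Recurrences managed without admission would lower the share, and repeated readmissions would raise it.

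**The case against.** The best defence is that the study is about the index admission. The outcomes objective ties length of stay, air leak and mortality to the SSP admission, and question 3 is limited to the inpatient stay. No question asks about readmissions or cumulative bed-days. The only outcome with a stated horizon, 6-month ipsilateral recurrence, is collected. The phrase about the study period may also mean calendar time rather than time per patient.

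Much of this stands for burden. A reader might infer that the study cannot answer its own burden question. The protocol does not support that, because it never defines burden as bed-days over 6 months, and an index-admission reading is coherent. Two further inferences also fail:

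- A reader might expect comparisons of ambulatory or short-stay care with inpatient care to be biased. No such comparison is planned, and care pathway is not among the evaluated parameters under Analyses.
- A reader might want a figure for bed-days missed per patient. The protocol gives no mean stay and no 6-month recurrence rate, so none can be derived.

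Nor is every early return lost. Recurrence is flagged at both reviews, and the 1-month interventions item is not restricted to the first admission.

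The defence does not cover surgery. Question 7 is untimed, the surgical objective includes recurrence management, and on no reading does the study period mean one month per patient. The index-admission reading also fails for stays beyond the 1-month review. The open wording belongs to the 1-month list only. The 26-week length-of-stay mark is unqualified in the schedule, but the text limits it to the initial stay. An analysis plan cannot recover data that were never collected.

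**Conclusion.** The point holds for surgery and procedures. As written, those after the 1-month review are not captured, including in patients whose initial stay runs past it. A 6-month surgery proportion is therefore biased low, and the analysis of its predictors is affected. The direction is certain only relative to a 6-month proportion; a proportion explicitly defined to 1 month would not be biased in this way.

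For healthcare burden the conclusion is narrower: the result will describe the index admission, and readmission bed-days are absent. The size of either shortfall cannot be derived from the protocol. The surgery figures (20% falling to between 18% and 10%) and the bed-day shares (17% to 33%) rest on assumed inputs and show scale only.

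This merits a change to the protocol because the objectives are already there and the remedy is cheap.

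**What to change.** Either extend the collection or narrow the claim.

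**Extend.** At the 6-month review, record surgical referral, surgery and pleural procedures since the 1-month review, with dates, and the admission and discharge dates of any pneumothorax-related readmission. Readmissions in the first month should be included, since their bed-days are not taken at the 1-month review either. Tick the interventions row at 26 weeks, and make the length-of-stay row say whether it means the initial or the total stay. Report question 7 to 6 months, and burden as index stay plus readmission bed-days. If days alive and out of hospital is preferred, mortality must also be collected at 6 months; at present it is scheduled only at the first review.

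**Narrow.** Otherwise, state in the objectives and in question 7 that burden and surgery are index-admission or 1-month outcomes. If index-admission is chosen, procedures still need completing for stays that run past the 1-month review.

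**Cost.** Extending adds a few conditional eCRF fields, filled mainly for patients with a readmission or a later referral or procedure, at a record review already planned and without patient contact. Narrowing costs only wording, but gives up later surgery, including surgery for recurrence.
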